### **Inclusion Criteria**

Cohort 1 (LCS): Adults aged  $\geq 18$  years old (male or female); Able to provide written informed consent; previous SARS-CoV-2 infection (As some Australians contracted SARS-CoV-2 in countries that did not undertake testing in the early stages of the pandemic, some participants will not have a diagnosis by PCR. Inclusion with physician confirmed Long Covid is consistent with worldwide research practices for Long Covid studies); continuing chronic symptoms persisting for  $\geq 3$  months post-acute COVID-19 infection and not attributable to an alternative disease state.

Cohort 2 (POTS): Adults aged  $\geq 18$  years old (male or female); POTS diagnosis; Able to provide written informed consent; Diagnostic criteria for POTS met as per the following: 1. sustained heart rate elevation of  $\geq 30$  beats/min within 10 minutes. 2. No other secondary cause of these symptoms. 3. Absence of orthostatic hypotension 4. Symptomatology present for greater than 3 months

Cohort 3 (Healthy Control): Otherwise, healthy adults aged  $\geq 18$  years old (male or female); Able to provide written informed consent; absence of POTS diagnosis or previous SARS-CoV-2 infection.

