### **Exclusion:**

Non-consent for participation in study; pregnancy or lactation; other known causes of autonomic dysfunction; co-morbidities such as Type 1 Diabetes, Parkinson's disease, multiple sclerosis, alcoholism, drug addiction, malignant neoplasm, recent cerebrovascular accident or transient ischaemic attack, acquired brain injury; significant surgery within the last 3 months; unavailability for completion of all assessments as per the study protocol; non-English speaker; terminally ill with life expectancy  $< 12$  months.

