### **3.7 Where will participants be recruited or sourced from?**

Any use of snowball sampling for recruitment should only be in the passive form. That is participants may be asked to discuss the research with friends/contacts who they think may be interested in volunteering to be participants. Those new participants should then contact the research team to volunteer.

Participants will be recruited through social media forums that pertain to support of those with LCS. Administrators of social media platforms for LCS will be approached by senior investigators for permission to post information about the study with contact details for researchers. We recognised the selection bias associated with this method of recruitment, however given the extraordinary nature of the current pandemic and the lack of understanding of LCS and its associated diagnosis and aetiology, it would seem that this bias is justified by the urgent requirement for preliminary understanding of the condition. As this study looks to explore immune, inflammatory and cardiovascular changes rather than efficacy of interventions, the use of convenience sample is more tolerable.

In addition, consecutive patients with POTS who attend [name] practice and The University of Adelaide, Centre for Heart Rhythm Disorders will be recruited. Potential participants may be approached by a member of the clinic/study staff via email introducing the study and providing the plain language patient information sheet explaining the purpose of the study. Healthy controls will be recruited through flyers and posters placed within The University of Adelaide health and education campuses. In addition, healthy controls referred to CHRDC/CVC for investigation of heart arrhythmia (but found to have none) will be recruited via the above mentioned flyers. Advertisements will be placed on the SAHMRI and University of Adelaide facebook sites as per attachment 5.

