#### POTS participants

- Email detailing study outline will be sent to potentially eligible participants. PICF will be attached to the email and patients will be requested to make contact if they are interested in the study.
- University social media and private practice internet advertisements
- Private practice and university flyers (attachment 6)

LCS participants

- Through social media advertisement (attachment 4)

Healthy matched controls will be recruited from

- Patients referred for cardiac evaluation who are healthy via practice flyers (attachments 6)
- Through flyers located at the Centre for Heart Rhythm Disorders facilities in Norwood, Adelaide and North Terrace Campus, University of Adelaide and SAHMRI (attachment 6) As well as facebook pages monitored and run by these organisations to promote current research.

Recruitment Materials: The following materials will be used to recruit participants.

1. Participant Information Sheet in plain language
2. Patient Consent Form
3. Introductory email to POTS patients who attend our private clinic
4. Introductory email and advertisement for social media administrators of support group for those with Long Covid
5. University of Adelaide, SAHMRI and Private Practice internet advertisements
6. Flyers for University and Private Clinic advertisement

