**Before study testing day:**

In addition, all study participants will be sent a link to a health questionnaire and QoL surveys as listed below. These can be done at leisure and without time restriction to reduce the effects of inconvenience and survey fatigue.

1. Holter Monitor: All patients will undergo 24 hour ambulatory ECG, at home (adhesive electrodes placed on the skin and attached to a recording device). This measure will be used to determine heart rate variability; which is a measure of baseline autonomic tone. It will also help to exclude other alternative cardiac arrhythmias.
2. Echocardiogram requires the subject to undertake an ultrasound of the heart previous to the day of testing at the subject's convenience. This test is important for determining other secondary causes of symptoms due to structural cardiac changes. It requires a non-invasive ultra-sound of the heart and generally takes 15 minutes to complete. To determine associations of neuroendocrine function with changes to orthostatic filling volumes and cardiac measurements. Echocardiogram will be undertaken in the semi-fowler position and then in passive leg raise (45 degree) position after 90 seconds.
3. Demographic survey and Medical Health History including alcohol consumption, tobacco use. Past medical history, medications and allergies will be completed by the two symptomatic cohorts.

Controls will complete a health history and demographic survey to confirm absence of exclusion medical conditions and medications when attending for assessment.

4. Rand SF-36: 36 item short form survey which is commonly utilised to measure self-reported quality of life measures in adult patients.
5. EQ-5D/5L: Is a short survey utilised and validated to describe and value health across 5 domains.
6. COMPASS-31: 31 question composite autonomic scale which is utilised widely for use in autonomic research and practice. It addresses the domains of: orthostatic intolerance, vasomotor, secretomotor, gastrointestinal, bladder and pupillomotor function.
7. Fatigue Severity Score: A 9 item questionnaire that reports how fatigue interferes with certain activities and rates the severity of fatigue.
8. 5 Point hypermobility screen: Five questions related to hypermobility. A score  $>2/5$  suggests hypermobility (sens 85%, spec 90%)

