### Attachment 3: Introduction Email to POTS Clinic Patients

#### EMAIL OF INTRODUCTION

Date:

Dear \_\_\_\_\_,

You have been identified as a patient who has been diagnosed with Postural Orthostatic Tachycardia Syndrome (POTS). As you may be aware, POTS is a relatively underdiagnosed condition that may have significant impact on health outcomes for those who are affected by it. Associate [name] and his supervised PhD student [name] are undertaking a study to explore the cardiovascular, immune and inflammatory profile of people with both POTS and Long Covid Syndrome (LCS). LCS is a syndrome that some people get after Covid-19 infection. In some people it seems to present with similar symptoms as POTS. We would like to understand if there are similarities in the blood, urine and cardiovascular profile of those with POTS and LCS. You have been identified as a person who may be eligible for inclusion in this study. Attached to this email you will find a patient information sheet and consent form that explains the purposes, risks and benefits of participation.. Please read this information and discuss further with your support persons or family members before deciding your involvement. You may contact [name] or any of the listed researchers for more information before making your decision.

Regards,

Assoc/[name]  
[name]  
[name]  
[name]  
[name]

The University of Adelaide, Centre for Heart Rhythm Disorders,  
[[contact]](mailto:[contact])  
Approval Number: H-2021-053

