# Are You a Healthy Adult Willing to Volunteer for a Study Exploring 'Long Covid'?

**The University of Adelaide, Centre for Heart Rhythm Disorders are looking for men and women to participate in a research study to evaluate the cardiovascular, immune and inflammatory causes of 'Long Covid'.**

To qualify, participants in this study will be men and women who:

- ❖ Are 18 years or over
- ❖ Have no other significant illnesses
- ❖ Do not take regular medication apart from the contraception pill

**Please email [[contact]](mailto:[contact]) for more information and to find out if you are eligible to participate in the study.**

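### Controls may be drawn from patients referred to the heart-rhythm centre for suspected arrhythmia, and the only POTS-specific bar is lack of a diagnosis, so the comparisons with healthy controls may be biased

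*Protocol*

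**What the plan says.** Section 3.7 names, as one source of controls, patients of the centre's own practice: "healthy controls referred to CHRDC/CVC for investigation of heart arrhythmia (but found to have none) will be recruited". Section 3.8 lists the same source first among the control routes: "Patients referred for cardiac evaluation who are healthy via practice flyers (attachments 6". The other routes are flyers at the centre and on the university and SAHMRI campus, and those organisations' Facebook pages.

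Eligibility for Cohort 3 (section 3.6) opens with "Otherwise, healthy adults aged" 18 or over and requires "absence of POTS diagnosis or previous SARS-CoV-2 infection". The exclusions for all cohorts include "other known causes of autonomic dysfunction". Section 3.16 adds a check on the day: "Controls will complete a health history and demographic survey to confirm absence of exclusion medical conditions and medications when attending for assessment". The flyer for healthy volunteers asks that they "Have no other significant illnesses" and take no regular medicine other than the contraceptive pill.

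The table in section 2.5 gives all three cohorts the standing test, Holter, COMPASS-31 and OHQ. The haemodynamic criterion, a sustained rise of at least 30 beats/min inside 10 minutes, is written for Cohort 2 only. Attachment 3 tells patients that "POTS is a relatively underdiagnosed condition", and section 4.4 describes POTS as under-recognised, with late diagnosis.

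**The concern.** Someone sent to a heart-rhythm centre for suspected arrhythmia, in whom none is found, has had one explanation ruled out. A negative arrhythmia work-up is compatible with POTS: section 3.16 itself uses Holter recording partly to rule out other arrhythmias. This route may therefore select towards the condition under study, and lack of a diagnosis is a weak filter for a condition described as often missed.

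The other filters do not clearly close the gap. The protocol does not define otherwise healthy, and section 3.8 applies the word healthy to referred cardiac patients. An undiagnosed, untreated person has no known cause of autonomic dysfunction, takes no excluded medicine and can answer the flyer truthfully. The standing test is done in controls, but the protocol does not use it for their eligibility.

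Objectives 2 and 3 rest on comparisons with matched healthy controls for biomarkers, quality of life, symptoms, cognition and psychological well-being. If some controls share the physiology of the POTS cohort, the POTS-versus-control differences shrink, and a real difference could be reported as absent. A larger sample improves power but does not remove this bias. Section 3.7 admits selection bias in recruiting the Long COVID cohort but does not discuss it for controls.

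**Working it through.** **Inputs, all from section 3.3.** Orthostatic heart-rate change: healthy mean 26, SD 15.5; POTS mean 45, SD 19.4. Two-sided alpha 0.05, Satterthwaite t test, 15 per group for 80% power. Planned loss 20%; planned size 34 per group. The share f of controls with POTS-like physiology is not given anywhere; 10%, 20% and 30% are assumptions.

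**Step 1: reproduce the plan's power.** Standard error = √(15.5²/15 + 19.4²/15) = √(616.61/15) = 6.41. Noncentrality = 19/6.41 = 2.96. Power from the noncentral t with Satterthwaite degrees of freedom is 81.5%, which agrees with the stated 80%.

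**Step 2: evaluable number.** 34 × (1 − 0.20) = 27.2, so 27 per group. This is more than the 15 the calculation needs, because 34 is more than a 20% loss requires: 15/0.80 = 18.75, so 19 per group.

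**Step 3: effect on the difference.** Write μH for the healthy mean, μP for the patient group's mean and μC for the mean of the affected controls. The observed difference is (μP − μH) − f(μC − μH). It equals (1 − f)(μP − μH) only when μC = μP. For POTS versus controls, taking the affected controls to follow the plan's POTS distribution:

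- control mean = 26(1 − f) + 45f, so difference = 19(1 − f);
- control variance = (1 − f)·15.5² + f·19.4² + f(1 − f)·19².

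At f = 20%, the difference is 19 × 0.80 = 15.2 and the variance is 192.20 + 75.27 + 57.76 = 325.23, giving an SD of 18.03.

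| f (assumed) | Difference, bpm | Control SD | Power, 15 per group | Power, 27 per group | Power, 34 per group |
|---|---|---|---|---|---|
| 0 | 19.0 | 15.50 | 81.5% | 97.4% | 99.3% |
| 10% | 17.1 | 16.92 | 69.9% | 92.3% | 96.8% |
| 20% | 15.2 | 18.03 | 57.4% | 83.3% | 90.9% |
| 30% | 13.3 | 18.89 | 45.1% | 70.7% | 80.6% |

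A 20% share is 0.20 × 34 = 6.8, or about 7 controls.

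**Step 4: would excluding on heart rate alone work?** With the plan's healthy mean of 26 and SD of 15.5, and assuming normality, P(rise ≥ 30) = 1 − Φ(4/15.5) = 39.8%. About two in five healthy people would be removed. These are 30-minute values, whereas the study stand lasts 10 minutes (section 3.16), so the exact share would differ.

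**The case against.** The strongest reply is that several safeguards exist and the size of the problem is unknown. A reader might infer that controls need only lack a POTS diagnosis. The document does not support that: they must also be otherwise healthy, uninfected, free of the listed conditions and checked by health history. Nor does it say why patients were referred, or that symptoms stayed unexplained. The under-recognition remark in section 4.4 concerns the wider medical community, and a centre with its own POTS clinic may be better than most at spotting the condition. All of this is fair. It makes contamination possible rather than established.

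The share could also be small. Referral is one route of several. If a third of controls came that way (an assumption), an overall share of 20% would need 0.20/(1/3) = 60% of them to be affected. At 10% or 20%, the heart-rate contrast keeps more than 80% power with 27 per group. This stands, but only for that contrast: the protocol gives no power calculation for the biomarker, quality-of-life, cognitive or anxiety and depression comparisons. The margin also disappears if the group size is cut to what a 20% loss needs.

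Finally, controls do complete COMPASS-31, OHQ and the standing test, and the handling of an abnormal result may lie in an analysis plan not seen here. That is correct, so the protocol's silence does not show that such a person would remain in the control analysis. The route and the eligibility wording, however, are fixed in the protocol itself.

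**Conclusion.** The point holds for the comparisons with healthy controls in Objectives 2 and 3. The planned referral route, with lack of diagnosis as the only POTS-specific bar, may admit people with unrecognised orthostatic intolerance, and the likely effect on POTS versus controls is a bias towards no difference.

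Two stronger readings should be resisted. One is that every contrast shrinks. The primary objective estimates POTS prevalence within the Long COVID cohort and uses no controls, and neither do the comparisons among Long COVID with POTS, Long COVID without POTS, and POTS. The other is that every control contrast shrinks by the factor 1 − f. By the formula in step 3, that needs the affected controls to share the comparator's mean. For Long COVID without POTS versus controls, the bias could have another size or direction.

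The figures of 17.1, 15.2 and 13.3 bpm illustrate assumed shares and do not estimate what will happen. They rest on the plan's 30-minute distributions and on 27 evaluable per group. On that basis, heart-rate power falls below 80% somewhere between a 20% and a 30% share. This is a correctable weakness in the control source, and it does not threaten the primary result.

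**What to change.** Preferred: remove the arrhythmia or cardiac-referral route for controls from sections 3.7 and 3.8, and keep the campus, SAHMRI and online routes. Flyers shown to controls in the centre's own clinic rooms belong to the same route and should go with it.

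Alternative, if the route is kept: record each control's recruitment source, and repeat the control contrasts without clinic-referred controls.

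In either case, add a sensitivity analysis of the control contrasts that leaves out any control with both the heart-rate rise and symptoms on the study stand. Do not exclude on heart rate alone, for the reason in step 4. A general eligibility rule that controls be free of palpitations, presyncope or orthostatic symptoms is not advised. It would select controls on what COMPASS-31 and OHQ measure as outcomes, and could make the contrasts too large.

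Cost: a short wording amendment, one small extra analysis on data largely collected already (recruitment source is the new item if the route stays), and perhaps slightly slower recruitment of 34 controls.

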### **3.8 What materials will be used to recruit participants and how will they be used?**

Provide details of any posters, flyers, participant information sheets, consent forms, advertisements, emails and letters that will be used. Include a listing of any online or physical sites the advertisements will be posted. See *National Statement Chapter 3.1.20*.

#### POTS participants

- Email detailing study outline will be sent to potentially eligible participants. PICF will be attached to the email and patients will be requested to make contact if they are interested in the study.
- University social media and private practice internet advertisements
- Private practice and university flyers (attachment 6)

LCS participants

- Through social media advertisement (attachment 4)

Healthy matched controls will be recruited from

- Patients referred for cardiac evaluation who are healthy via practice flyers (attachments 6)
- Through flyers located at the Centre for Heart Rhythm Disorders facilities in Norwood, Adelaide and North Terrace Campus, University of Adelaide and SAHMRI (attachment 6) As well as facebook pages monitored and run by these organisations to promote current research.

Recruitment Materials: The following materials will be used to recruit participants.

1. Participant Information Sheet in plain language
2. Patient Consent Form
3. Introductory email to POTS patients who attend our private clinic
4. Introductory email and advertisement for social media administrators of support group for those with Long Covid
5. University of Adelaide, SAHMRI and Private Practice internet advertisements
6. Flyers for University and Private Clinic advertisement

### 3.9 How and by whom will initial contact with participants be made?

If recruitment is to be conducted by a third party, please describe how this will take place. Any use of snowball sampling for recruitment should only be in the passive form. That is participants may be asked to discuss the research with friends/contacts who they think may be interested in volunteering to be participants. Those new participants should then contact the research team to volunteer.

It is generally preferred initial contact is made in low pressure ways, such as email or post. If the initial approach will be made in another way, e.g. face to face, provide a justification.

Researchers named on this application will screen the Centre for Heart Rhythm Disorders POTS database for patients who attend the POTS clinic and who may meet the inclusion criteria. Those identified from the clinic as potential participants will be invited by email (See attachment 3). Some of the participants will be known to investigators through clinical practice. Potential participants will be provided with plain language statements (see attachment 1) explaining the purpose of the study and the benefits and/or risks of involvement. They will be given opportunity to discuss with family and support persons and invited to contact the research team for more information before making a decision to participate.

Those with LCS who respond to social media notices (see attachment: 4) requesting more information will be sent a plain language statement by [name] (PhD Candidate) via email and invited to discuss the study by telephone with a senior investigators before making a decision to consent to participation. Once this has been done formal arrangements for an appointment will be made for consent and enrolment in this study.

A description of the study will be placed on the University of Adelaide, Centre for Heart Rhythm Disorders and SAHMRI internet site as well as social media sites. (See attachment 5). Flyers will be placed at the Cardiovascular Centre Private Clinic as well as appropriate spaces at the University of Adelaide notice boards (See attachment 6). Those who respond to these advertisements via email will be sent a study PICF and offered an opportunity to discuss via phone with researchers.

### 3.10 Will any personal information including names, contact details, email addresses of participants etc. be accessed for purposes of recruitment? If yes, outline how and by whom this information will be accessed:

Researchers must ensure that personal information is not accessed without the consent of the individual.

Only patients who have registered and seen a cardiologist at The Centre for Heart Rhythm Disorders will be contacted using contact details patients have already registered with the Centre. These details will only be accessed by the researchers in this study (who work at The Centre for Heart Rhythm Disorders). Recorded details will remain on site and will not be removed.

In the cases of volunteers as controls and LCS cohort; they will contact the researchers and provide

consent for their details to be stored at The Centre for Heart Rhythm Disorders on a secure, password protected database.

### 3.11 Describe how, when and what information about the proposed research activities will be provided to participants and any third parties:

A person's decision to participate in research must be based on sufficient information, an understanding of research and the implications of participation. Use of the [participant information sheet](#) (which includes contacts for complaints) and consent form templates which cover the information required by the *National Statement* is required. For online surveys, the information sheet must be incorporated into the survey preamble. Where research is being conducted overseas, it would be helpful to participants if a local, 'independent' person is also included as a contact for complaint. These documents are to be attached to the application. See *National Statement Chapter 2.2*.

Potential study participants will be provided with a participant information sheet (See Attachment 1) via email or during a visit to the POTS clinic. Participants will be encouraged to discuss the involvement in the study with family and support persons before returning a signed consent form to the principal researcher. Participants will also be given the opportunity to ask direct questions of researchers in regard to participation, before deciding to consent to involvement in the study. All participants will be familiarised with the facility and given further opportunity to ask questions when they arrive for the study. They will be given another opportunity to withdraw from the study after they have been familiarised with the protocol. Participants will be reassured that withdrawal will not affect continuation of medical treatment.

Please see attached participant information sheet and consent form. (Attachment 1 and 2 respectively)

